5.3. DETAILED DATA REVIEW TIMEFRAME

Table E Detailed Timeframe for BDR indicates estimated timings for the data review activities, as well as the person(s) responsible for each activity (“Owner”).

Table E Detailed Timeframe for BDR Process

No.	Activity	Owner	Relative Timeframe
1	Data transfer of the clean database to STL (with minimal list of open queries if agreed with STL).	DTL	At least 1 week prior to final data review

Document: \\ieedc-vnasc01\BIOSdata\Abivax\ABX464\FZA92720\Biostatistics\Documentation\SAP\ABX464-103_SAP_V2.0_10MAY2021

Author: [REDACTED]

Version Number: 2.0
Version Date: 10May2021

Template No.: CS_TP_BS016 Revision 5

Reference: CS_WI_BS005

Effective Date: 01Apr2018

			meeting.
2	Provide the data handling report to STL.	DTL	1-2 weeks prior to final data review meeting.
3	Check that the coding has been approved by Abivax and that the reconciliation of the non-eCRF data and of the SAEs has been performed and documented.	DTL	
4	Collect any further necessary input from CPM/PL and DTL.	STL	
5	Preparation and distribution of the draft DR report and other statistics deliverables to CRT.	STL	At least 2 business days prior to final data review meeting.
7	Review all deliverables and the draft DR report.	CRT	
8	Facilitate the data review meeting.	STL	Not applicable
9	Preparation of final data review report.	STL	3 to 4 business days following final data review meeting, prior to DBL.
10	Approval of final data review report.	Abivax	
11	Distribution of the signed data review report in PDF format to CRT.	STL	

6. GENERAL CONSIDERATIONS

6.1. REFERENCE START DATE AND STUDY DAY

Study Day will be calculated from the reference start date and will be used to show start/stop day of assessments and events.

Reference start date is defined as the day of the first dose of study medication. (Day 1 is the day of the first dose of study medication).

- If the date of the event is on or after the reference date, then:

$$\text{Study Day} = (\text{date of event} - \text{reference date}) + 1$$

Document: \\ieddc-vnasc01\BIOSdata\Abivax\ABX464\FZA92720\Biostatistics\Documentation\SAP\ABX464-103_SAP_V2.0_10MAY2021

Author: [REDACTED]

Version Number: 2.0
 Version Date: 10May2021

Template No.: CS_TP_BS016 Revision 5

Reference: CS_WI_BS005

Effective Date: 01Apr2018

- If the date of the event is prior to the reference date, then:
Study Day = (date of event – reference date).

In the situation where the event date is partial or missing, Study Day and any corresponding durations will appear missing in the listings.

6.2. BASELINE

Unless otherwise specified, baseline is defined as the last non-missing measurement taken prior to reference start date (including unscheduled assessments). In the case where the last non-missing measurement and the reference start date coincide, that measurement will be considered pre-baseline, but Adverse Events (AEs) and concomitant medications commencing on the reference start date will be considered post-baseline.

6.3. RETESTS, UNSCHEDULED VISITS AND EARLY TERMINATION DATA

In general, for by-visit summaries, data recorded at the nominal visit will be presented. Unscheduled measurements will not be included in by-visit summaries but will contribute to the best/worst case value where required (e.g. shift table).

In the case of a retest (same visit number assigned), the last available measurement for that visit will be used for by-visit summaries.

Early discontinuation data will be mapped to the next available visit number for by-visit summaries. Listings will include scheduled, unscheduled, retest and early discontinuation data.

Document: \\ieddc-vnasc01\BIOSdata\Abivax\ABX464\FZA92720\Biostatistics\Documentation\SAP\ABX464-103_SAP_V2.0_10MAY2021

Author: [REDACTED] Version Number: 2.0
Version Date: 10May2021

Template No.: CS_TP_BS016 Revision 5

Reference: CS_WI_BS005

Effective Date: 01Apr2018

6.4. WINDOWING CONVENTIONS

There will be no visit windowing applied in this study.

6.5. STATISTICAL TESTS

The default significant level will be 5%; confidence intervals (CI) will be 95% and all tests will be two-sided, unless otherwise specified in the description of the analyses.

6.6. COMMON CALCULATIONS

For quantitative measurements, change from baseline will be calculated as:

- Test Value at Visit X – Baseline Value

A patient will be considered to have a reduction relative to baseline in variable X at Visit X when change from baseline for variable X is less than zero.

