2.4. Secondary Endpoints

The secondary endpoints of this study are:

- Number and rate of patients in clinical remission at Week 8, per each intervention/treatment group. Clinical remission, based on the Mayo Scoring system, is defined as stool frequency subscore = 0 or 1 and rectal bleeding subscore = 0 and endoscopy subscore = 0 or 1 (modified to exclude friability).

- Combined number and rate of patients in clinical remission at Week 8 and at Week 16, per each intervention/treatment group.
- Number and rate of patients with clinical response at Week 8 and Week 16 per intervention/treatment group. Clinical Response is defined as a reduction in Mayo Score of at least 2 points and greater than or equal to 30 percent from baseline with an accompanying decrease in rectal bleeding sub-score of greater than or equal to 1 point or absolute rectal bleeding sub-score of less than or equal to 1 point.
- Number and rate of patients with endoscopic improvement, by segment, and number and rate of patients with endoscopic remission, by segment, at Week 8 and at Week 16 (if available) per intervention/treatment group. Endoscopic improvement is defined as a Mayo endoscopic sub score of ≤1 (excluding friability) and endoscopic remission defined as sub score of 0.
- Number and rate of patients with mucosal healing. Mucosal healing is defined as both endoscopic remission and histological remission (Geboes score < 2.0).
- Reduction relative to baseline in stool and rectal bleeding frequency at every study visit by ABX464 dose group and versus placebo.
- Reduction relative to baseline in partial Modified Mayo Score at every study visit and Modified Mayo Score at Week 16 (if available) by ABX464 dose group and versus placebo.
- Reduction relative to baseline in fecal calprotectin and CRP levels at Week 8 and Week 16 by intervention/treatment group.
- Change relative to baseline in miRNA-124 expression in rectal/sigmoidal biopsies at Week 8 and Week 16 (if available) and in total blood at every timepoints by intervention/treatment group.
- The scores and changes from baseline in IBDQ at Week 8 and Week 16 per intervention treatment group.
- Reduction relative to baseline of infiltrate/histopathology (rectal/sigmoidal biopsies) using the Robarts Histopathology Index (RHI), the Geboes and Nancy Histology Scoring Scales at Week 8 and Week 16 (if available) per intervention/treatment group.

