15. EFFICACY OUTCOMES

15.1. PRIMARY EFFICACY

15.1.1. PRIMARY EFFICACY VARIABLE & DERIVATION

The primary efficacy variable is the reduction from baseline in MMS at Week 8 (Day 57).

The MMS will be obtained from the MMS eCRF page with raw.MMS.MMSSCR and confirmed by eDiary entries. The MMS ranges from 0 to 9 and is derived from the sum of 3 sub-scores ranging from 0 to 3 for stool frequency, rectal bleeding and mucosal appearance at endoscopy respectively, with a lower score indicating less severe or no ulcerative colitis (UC) (See APPENDIX 2). The MMS determined at screening will be used as baseline MMS, as MMS is not calculated at Day 1.

Change from baseline is described in Section 6.6.

Document: \\ieedc-vnasc01\BIOSdata\Abivax\ABX464\FZA92720\Biostatistics\Documentation\SAP\ABX464-103_SAP_V2.0_10MAY2021

Author: [REDACTED]

Version Number: 2.0
Version Date: 10May2021

Template No.: CS_TP_BS016 Revision 5

Reference: CS_WI_BS005

Effective Date: 01Apr2018

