15.2.1.6. Reduction Relative to Baseline in Stool Frequency and Rectal Bleeding

Number and percentage of patients in each Mayo stool frequency category will be summarized at every study visit and the number of patients with reduction in stool frequency sub-score relative to baseline will be recorded. The stool frequency sub-score corresponds to the **average** of the 3 most recent daily stool frequencies prior to the visit, rounded to the nearest whole number. The normal stool frequency is subtracted from this average to obtain the Mayo stool frequency sub-score for a particular visit. Frequency of stools will be obtained from e-Diaries completed daily by the patient.

Descriptive statistics for stool frequency sub-score and its change from baseline will be presented by visit.

Document: \\iedc-vnasc01\BIOSdata\Abivax\ABX464\FZA92720\Biostatistics\Documentation\SAP\ABX464-103_SAP_V2.0_10MAY2021

Author: [REDACTED] Version Number: 2.0
Version Date: 10May2021

Template No.: CS_TP_BS016 Revision 5

Reference: CS_WI_BS005

Effective Date: 01Apr2018

The frequency sub-score will be calculated as described above. Reduction relative to baseline is defined in Section 6.6.

Number and percentage of patients in each rectal bleeding category will be summarized. The number of patients indicating an improvement in rectal bleeding sub-score from the baseline rectal bleeding sub-score will be recorded. The rectal bleeding sub-score corresponds to the **worst category** of the 3 most recent values prior to the visit.

Only days when both the number of stool and the rectal bleeding are available will be considered for the calculation. If some data are missing from the most recent consecutive 3 days preceding the visit, then data from the next closest days within 7 days before the visit will be used for calculation.

15.2.1.7. Reduction Relative to Baseline in pMMS at every Visit and MMS at Week 16

Partial MMS will be assessed at every visit, and MMS at Screening, Week 8 and Week 16. Partial MMS is the sum of the stool frequency and rectal bleeding sub-scores of the MMS.

The screening MMS will be used as baseline MMS. Day 1 pMMS will be used as baseline pMMS. Absolute scores and change from baseline will be summarized by treatment arm, and the number of patients with a reduction relative to baseline in the scores will be recorded. Reduction relative to baseline is defined in Section 6.6

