15.2.3. ANALYSIS OF SECONDARY EFFICACY VARIABLES

15.2.3.1. Analysis of Secondary Variables at Week 8 and at Week 16

In addition to the descriptive statistics as described in Section 15.2 and specific subsections of Section 15.2. ANCOVA models, using the same procedure as described for the primary efficacy analysis in section 15.1.3, will be used to make the assessments listed below:

- Global effect of ABX464 treatment vs placebo in change from baseline in MMS at Week 8
- Combined number and percentage of patients in clinical remission at Week 8 and Week 16
- The number and percentage of patients with clinical response at Week 8 and Week 16
- The number and percentage of patients with endoscopic improvement and remission, by segment at Week 8 and Week 16
- Proportion of patients with mucosal healing at Week 8 and Week 16
- Daily stool frequency and number of patients with reduction relative to baseline in stool frequency sub-score at every study visit
- Number of patients with reduction relative to baseline in rectal bleeding sub-score at each visit
- Frequencies and percentages for rectal bleeding and stool frequency sub-score categories
- Frequencies and percentages for Mucosal Appearance at endoscopy by segment
- Total IBDQ scores and change from baseline at Week 8 and Week 16

In addition, the above variables will be included in a listing by patient. The frequency of daily stools and categories of rectal bleeding as recorded in the e-Diary will be listed for the duration of the study.

[REDACTED]

[REDACTED]

[REDACTED]

Document: \\ieddc-vnasc01\BIOSdata\Abivax\ABX464\FZA92720\Biostatistics\Documentation\SAP\ABX464-103_SAP_V2.0_10MAY2021

Author: [REDACTED]

Version Number: 2.0
Version Date: 10May2021

Template No.: CS_TP_BS016 Revision 5

Reference: CS_WI_BS005

Effective Date: 01Apr2018

15.2.3.2. Analysis of Number and Percentage of Patients in Clinical Remission at Week 8

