15.2.3.3. Analysis of Secondary Variables Measured Repeatedly Over Time

In addition to descriptive statistics as described in Section 15.2, mixed model repeated measures ANCOVA will be used to assess the following secondary variables:

- Change from screening in MMS to Week 8 and Week 16 and change from baseline to all post-baseline visits in pMMS during the study, by treatment group vs placebo group.
- The change from baseline in fecal calprotectin levels at Week 8 and Week 16.
- The change from screening in the histopathology/infiltrate (rectal biopsies) assessed by the Robarts Histopathology Index, the Geboes and Nancy Histology Scoring Scales at Week 8 and Week 16 (if available).

Mixed Model for Repeated Measures (MMRM) will be used to analyze change from baseline in MMS, pMMS, fecal calprotectin, RHI, Geboes and Nancy scores. Change from baseline at the specified Week

Document: \\ieedc-vnasc01\BIOSdata\Abivax\ABX464\FZA92720\Biostatistics\Documentation\SAP\ABX464-103_SAP_V2.0_10MAY2021

Author: [REDACTED]

Version Number: 2.0
Version Date: 10May2021

Template No.: CS_TP_BS016 Revision 5

Reference: CS_WI_BS005

Effective Date: 01Apr2018

will be analyzed by using a MMRM model with baseline value as a covariate, fixed effects for treatment group, exposure to previous biologics or JAK inhibitors, visit, visit by treatment group interaction and a random error term. For the MMRM model, the Kenward-Roger method for approximating the denominator degrees of freedom and correcting for bias in the estimated variance-covariance of the fixed effects will be used. This will be achieved by specifying the DDFM = KR option in the MODEL statement within PROC MIXED. An unstructured covariance will be selected initially, and if convergence is not achieved with this structure, the following covariance structures will be used in the order listed until convergence is achieved: Toeplitz (TOEP), Autoregressive (AR) and Compound Symmetry (CS).

The strata US vs non-US sites will not be included as a factor in the model as the stratification occurs only because US patients will not receive 100 mg dose of ABX464.

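### Rectal bleeding is a versus-placebo secondary endpoint, but its sub-score is compared between arms only as a yes/no reduction count and as category frequencies, never as mean change

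*SAP*

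**What the plan says.** Protocol 2.4 lists as a secondary endpoint: "Reduction relative to baseline in stool and rectal bleeding frequency at every study visit by ABX464 dose group and versus placebo".

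SAP 6.6 makes reduction a yes/no property: a patient has a "reduction relative to baseline in variable X at Visit X when change from baseline for variable X is less than zero". SAP 15.2.3.1 lists the assessments to be made with the ANCOVA procedure of the primary analysis. Its rectal-bleeding items are:

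- "Number of patients with reduction relative to baseline in rectal bleeding sub-score at each visit";
- frequencies and percentages in the sub-score categories.

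For stool the item is wider: "Daily stool frequency and number of patients with reduction relative to baseline in stool frequency sub-score at every study visit". SAP 15.2.1.6 adds: "Descriptive statistics for stool frequency sub-score and its change from baseline will be presented by visit". It makes no matching statement for bleeding, where it names category counts and the number of improvers. The bleeding sub-score is the worst category "of the 3 most recent values prior to the visit".

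The MMRM of SAP 15.2.3.3 covers MMS, pMMS, fecal calprotectin, RHI, Geboes and Nancy scores. It includes "change from baseline to all post-baseline visits in pMMS during the study, by treatment group vs placebo group", but neither sub-score alone. SAP 7.1 lists baseline MMS and baseline pMMS as covariates, but no sub-score baseline.

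**The concern.** A graded outcome is collected at every visit, and the protocol promises a comparison with placebo. The plan then reduces the bleeding score to whether it fell at all. This has two consequences:

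- **Size of change is lost.** A fall from 3 to 2 counts the same as a fall from 3 to 0.
- **Patients at the floor count as non-reducers.** A patient who starts at 0 and stays there has no reduction, and no denominator rule addresses this.

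At stake is the sensitivity of a listed secondary endpoint. A real dose effect on bleeding could go undetected when the data to show it are already in the database.

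**Working it through.** **1. The plan's own power figure.** Protocol 9.4 assumes mean MMS reductions of 2.5 and 1.0, SD 2.1, two-sided 5%, 5% dropout and 58 randomized per arm. The two-sample t-test needs 43 per arm for 90% power, or 43/0.95, rounded up to 46, after dropout. With 58 × 0.95 ≈ 55 evaluable, power is 96.0%, so the stated power above 90% reproduces. It concerns MMS only. The documents state no effect, SD or power for bleeding.

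**2. What the flag means on this score.** The MMS is the "sum of 3 sub-scores ranging from 0 to 3 for stool frequency, rectal bleeding and mucosal appearance at endoscopy respectively". Sub-scores are whole numbers, so a change below zero is a fall of at least 1 point.

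**3. Who starts at the floor.** Entry requires MMS 5 to 9 with endoscopy 2 or 3 (Protocol 4.2.1). That allows 23 combinations of (stool, bleeding, endoscopy). Three have bleeding 0: (2,0,3), (3,0,2) and (3,0,3). SAP 5.2.4 accepts MMS 4 for patients enrolled under the original protocol. This adds five combinations, two with bleeding 0, namely (2,0,2) and (1,0,3), giving 5 of 28. These are counts of possible scores at screening, not proportions of patients.

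**4. Assumptions for the power comparison** (none is in the documents):

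- The MMS effect is split equally over three sub-scores: placebo 1.0/3 = 0.33, active 2.5/3 = 0.83, difference 0.50.
- The SD of sub-score change runs from 2.1/3 = 0.7 (sub-scores move together) to 2.1/√3 = 1.21 (independent).
- Baseline bleeding B is drawn uniformly over the 23 combinations.
- There are 58 per arm.

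The Week 8 score is W = B − δ + ε, with δ the arm's mean reduction and ε normal with the stated SD, rounded and bounded to 0–3. Two outcomes go into the same ANCOVA with terms for arm and baseline bleeding: the flag (1 if W − B < 0, otherwise 0) and the change W − B. Power is the share of simulated trials with p < 0.05. With 4,000 trials the Monte Carlo standard error is at most √(0.25/4000) = 0.8 points.

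| SD of change | Flag | Mean change | Loss (points) |
|---|---|---|---|
| 0.7 | 79% | 89% | 10 |
| 1.0 | 49–50% | 63–65% | 14–15 |
| 1.21 | 35–37% | 48–49% | 12–13 |

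Ranges are over repeated runs. Both sides are adjusted for baseline bleeding. The plan does not do this for the flag, since the primary procedure adjusts for baseline MMS, so the comparison is not tilted against the flag.

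**5. A second baseline distribution.** With baselines of 1, 2 and 3 weighted 25%, 40% and 35%, and error SD 0.8 to 1.0, mean change has 84% to 67% power and the flag 75% to 57%. With 10% entering at 0, the figures are 82% to 64% against 69% to 50%. The loss is about 10 points without floor patients and 13 to 14 with them.

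**The case against.** The best defence is that the graded information is not lost from the plan. pMMS, the sum of the stool and bleeding sub-scores, is modelled as change from baseline against placebo at every post-baseline visit. Daily stool frequency is in the ANCOVA list, stool sub-score change is summarised by visit, and category frequencies keep the grading. SAP 15.2 also allows descriptive change from baseline for secondary variables where relevant. The endpoint lies outside the gatekeeping sequence, and no power was claimed for it. All of this stands. It confines the gap largely to bleeding, because pMMS cannot show which of its two components moved.

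The floor is not peculiar to the flag: a patient at 0 cannot improve on mean change either. That stands too, although a model with the sub-score's own baseline takes account of it.

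A reader might infer more than the documents support:

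- **That any change, however small, counts.** This is not so for the sub-scores, where the smallest fall is 1 point. The plan uses the same 1-point step for bleeding in its clinical-response definition.
- **That noise alone makes 21–30% of patients reducers.** Under symmetric error the rate is (1 − agreement)/2, so 21–30% requires test–retest agreement of only 58% to 40%. At 90% agreement it is 5%. Plausible inputs give about 4–31%, and the documents fix none of them.
- **That the zero threshold damages the MMS, pMMS, calprotectin, CRP and histology results.** Those reduction counts are only recorded (SAP 15.2.1.7, 15.2.1.9, 15.2.1.11) and are not in the comparison list of 15.2.3.1. All but CRP are also modelled as mean change.
- **That false positives increase.** Misclassification falls on all arms alike. It dilutes the contrast and does not inflate type I error.

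**Conclusion.** The point holds for rectal bleeding. A versus-placebo secondary endpoint is compared through a yes/no flag and category frequencies, with no named comparison of mean change outside pMMS and no adjustment for the sub-score's own baseline. The cost is about 10 to 15 points of power for a dose-versus-placebo comparison. That figure depends on the equal split of the MMS effect, the SD range and the assumed baseline distribution. The direction was the same in every setting tried, but the size is illustrative. The stool sub-score shares the flag but keeps quantitative analyses. The primary endpoint and the dose-testing sequence are unaffected, so this is a modest and worthwhile improvement to a secondary analysis.

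**What to change.** - In SAP 15.2.3.3, add change from baseline in the rectal-bleeding sub-score to the MMRM, with its own baseline as covariate, as the versus-placebo comparison for this endpoint. Add the stool-frequency sub-score in the same way for consistency.
- Add both sub-score baselines to the covariate list in SAP 7.1, and state which visit supplies them.
- In SAP 15.2.3.1, keep the reduction counts as descriptive. Show them for the full analysis set and also among patients with a baseline sub-score of at least 1.

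The cost is SAP wording and two more runs of a model already specified, with no new data. The downside is two more sets of secondary p-values, to be read descriptively, as Protocol 9.2 already says for its mixed-model analyses.

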6.7. SOFTWARE VERSION

All derivations, statistical analyses, summaries, and listings will be generated using SAS® version 9.2 or higher (SAS® Institute, Inc., Cary, North Carolina). Graphics will be prepared using the same versions of SAS®.

7. STATISTICAL CONSIDERATIONS

Summaries will include descriptive statistics for continuous variables (sample size [n], mean, standard deviation [SD], median, minimum and maximum) and for categorical variables (frequency [n] and percentage), unless otherwise stated in the relevant section. Percentages will be based on the number of

Document: \\iedc-vnasc01\BIOSdata\Abivax\ABX464\FZA92720\Biostatistics\Documentation\SAP\ABX464-103_SAP_V2.0_10MAY2021

Author: [REDACTED] Version Number: 2.0
Version Date: 10May2021

Template No.: CS_TP_BS016 Revision 5

Reference: CS_WI_BS005

Effective Date: 01Apr2018

subjects within the relevant analysis set and treatment arm, or the number of subjects with data available where relevant.

If the original data has N decimal places, then the summary statistics will have the following decimal places:

Minimum and maximum: N

Mean, median, confidence intervals, ratios: N + 1

SD: N + 2

Percentages will be reported to one decimal place. P-values should be reported to three decimal places, except values <1.000 but >0.999 will be presented as ‘>0.999’ (e.g., 0.9998 is presented as >0.999); and values <0.001 will be presented as ‘<0.001’ (e.g., 0.0009 is presented as <0.001)

